	
CR=complete response; FLC=free light chain; IMWG=International Myeloma Working Group; M-protein=monoclonal paraprotein; MR=minimal response; PC=plasma cell; PD=progressive disease; PR=partial response; sCR=stringent complete response; SD=stable disease; VGPR=very good partial response
 
All response categories (CR, sCR, VGPR, PR, and PD) require 2 consecutive assessments made at any time before the institution of any new therapy; CR, sCR, VGPR, PR, and SD categories also require no known evidence of progressive or new bone lesions if radiographic studies were performed. VGPR and CR categories require serum and urine studies regardless of whether disease at baseline was measurable on serum, urine, both, or neither.
 
Radiographic studies are not required to satisfy these response requirements. Bone marrow assessments need not be confirmed. For PD, serum M-component increases of more than or equal to 1 g/dL are sufficient to define relapse if starting M-component is ≥ 5 g/dL.
 
* Clarifications to IMWG criteria for coding CR and VGPR in subjects in whom the only measurable disease is by serum FLC levels: CR in such subjects indicates a normal FLC ratio of 0.26 to 1.65 in addition to CR criteria listed above. VGPR in such subjects requires a >90% decrease in the difference between involved and uninvolved FLC levels.
 
† Clarifications to IMWG criteria for coding PD: Bone marrow criteria for PD are to be used only in subjects without measurable disease by M protein and by FLC levels; “25% increase” refers to M protein, FLC, and bone marrow results, and does not refer to bone lesions, soft tissue plasmacytomas, or hypercalcemia and the “lowest response value” does not need to be a confirmed value.
 
^a Presence/absence of clonal cells is based upon the kappa/lambda ratio. An abnormal kappa/lambda ratio by immunohistochemistry or immunofluorescence requires a minimum of 100 plasma cells for analysis. An abnormal ratio reflecting presence of an abnormal clone is kappa/lambda of >4:1 or <1:2.
 
Clinical Relapse
 
Clinical relapse is defined using the definition of clinical relapse in IMWG criteria (Durie 2006⁷; Kumar 2016¹¹; Rajkumar 2011²²). In IMWG criteria, clinical relapse is defined as requiring one or more of the following direct indicators of increasing disease or end-organ dysfunction that are considered related to the underlying plasma cell proliferative disorder:
 
 1. Development of new soft tissue plasmacytomas or bone lesions on skeletal survey, magnetic resonance imaging, or other imaging 2. Definite increase in the size of existing plasmacytomas or bone lesions. A definite increase is defined as a 50% (and at least 1 cm) increase as measured serially by the sum of the products of the cross-diameters of the measurable lesion 3. Hypercalcemia (>11.5 mg/dL; >2.875mM/L) 4. Decrease in hemoglobin of more than 2 g/dL (1.25 mM) or to less than 10 g/dL 5. Rise in serum creatinine by more than or equal to 2 mg/dL (≥ 177 mM/L) 6. Hyperviscosity 
In some subjects, bone pain may be the initial symptom of relapse in the absence of any of the above features. However, bone pain without imaging confirmation is not adequate to meet these criteria in studies.

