
M-protein levels need to meet the definition of disease progression (see [Table 5](#)) for subjects to have disease progression. Disease evaluations will continue beyond relapse from CR until disease progression is confirmed.

Disease progression must be consistently documented across clinical study sites using the criteria in [Table 5](#). It is important that instances of disease progression be reported to the sponsor as soon as possible. Diagnosis and documentation of disease progression will be reported to the sponsor within 24 hours of suspected disease progression. The medical monitor will review the information to confirm that the IMWG criteria for disease progression have been met. If the medical monitor agrees that disease progression has occurred, then a confirmation will be returned to the investigator, and the subject will be withdrawn from study treatment. If the medical monitor considers that the IMWG criteria for disease progression have not been met, then the medical monitor will contact the investigator to discuss the subject.

For continuation of treatment, the IMWG response will be determined on an ongoing basis by the investigator. For data analysis and reporting, however, the sponsor will use a validated computer algorithm that has been shown to provide consistent review of the data necessary to determine disease progression and response according to IMWG criteria.

For subjects who discontinue study treatment before disease progression, disease evaluations should continue to be performed as described in the Time and Events Schedule, until confirmed disease progression, death, start of a new treatment for multiple myeloma, withdrawal of consent for study participation, or the end of the data collection period, whichever occurs first. Blood and urine for disease evaluations scheduled for treatment days should be collected before study treatment is administered.

Refer to [Attachment 13](#) details on efficacy evaluations after the end of the data collection period.

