#### **2.7.4. First Subsequent Anticancer Therapy Start Date**

If the start date of the first subsequent anticancer therapy is completely missing or the month is missing, no imputation will be performed. If only the day of the first subsequent therapy start date is missing, the following imputation rules will be applied:

- If the month and year of the start date are the same as the month and year of the last dosing date, the day of last dosing date +1 or the day-component of the stop date of subsequent anticancer therapy will be imputed, whichever is earlier.
- If the month and year of the start date are not the same as the month and year of last dosing date, the first day of the month will be imputed.

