**Table 2: PFS Event and Censoring Method**

Situation	Date of Progression or Censoring	Outcome
No postbaseline disease assessment	Randomization	Censored
Disease progression at or prior to start of subsequent anticancer therapy	Earliest date that indicates disease progression	PFS event
Death at or prior to start of subsequent anticancer therapy	Date of death	PFS event
Other, such as: Withdrawal of consent to study participation, Lost to follow-up Start of subsequent anticancer therapy prior to disease progression or death	Date of last disease assessment prior to withdrawal of consent to study participation, lost to follow-up, or start of subsequent anticancer therapy	Censored

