### **6.1. Adverse Events**

AEs will be recorded in standard medical terminology and graded according to the National Cancer Institute Common Terminology Criteria for Adverse Events (NCI-CTCAE), Version 4.03. For AE reporting, the verbatim term used in the CRF by investigators to identify adverse events will be coded using the latest version of Medical Dictionary for Regulatory Activities (MedDRA) coding dictionary.

The relationships to study medication will be recorded as not related, doubtful, possible, probable, or very likely on eCRF for all the AEs. Adverse events will be categorized and summarized according to their highest relationship to study medication. An adverse event is considered as related to study medication if the relationship is recorded as possible, probable or very likely.

Treatment-emergent adverse events (TEAEs) are defined as any AE with onset date and time on or after that of the first dose through 30 days after the last study drug administration, or the day prior to start of subsequent therapy, whichever is earlier; or the follow-up AE (linked to an existing TEAE) with onset date and time beyond 30 days after the last study agent administration but prior to the start of subsequent therapy; or any AE that is considered related to (very likely, probably, or possibly related) study medication regardless of the start date of the event; or any AE that is present at baseline but worsens in toxicity grade or is subsequently considered drug-related by the investigator. AEs with missing or partial onset date and time will be considered as treatment-emergent unless the onset date and time of an AE can be determined as earlier than that of the first dose, or later than 30 days after last study drug administration.

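### A next-therapy start with a missing day (SAP 2.7.4) can be imputed before a documented progression in the same month, so that a true PFS event is censored

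*SAP*

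**What the plan says.** SAP 2.7.4 gives two rules: "If only the day of the first subsequent therapy start date is missing, the following imputation rules will be applied". If the therapy started in the same month and year as the last dose, "the day of last dosing date +1 or the day-component of the stop date of subsequent anticancer therapy will be imputed, whichever is earlier". Where its month and year "are not the same as the month and year of last dosing date, the first day of the month will be imputed". No disease-assessment date enters either rule.

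The imputed date then decides PFS. SAP Table 2 (section 5.3.1) lists as an event "Disease progression at or prior to start of subsequent anticancer therapy". It lists among the censored situations "Start of subsequent anticancer therapy prior to disease progression or death", dated at the last disease assessment before that start. SAP 5.3.7.1 censors duration of response (DOR) in the same way.

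Protocol Table 5 (section 9.2.1) adds that the response categories, progression included, "require 2 consecutive assessments made at any time before the institution of any new therapy". For subjects who stop study treatment before progression, Protocol 9.2.1 continues disease evaluations "until confirmed disease progression, death, start of a new treatment for multiple myeloma".

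**The concern.** Both rules choose an early day in the month. A subject who progresses and changes therapy within one calendar month can be given a therapy start that precedes the progression. Table 2 then turns a documented event into a censoring at the previous assessment.

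The subject's own record usually argues against such a date. Because evaluations are meant to stop when new treatment starts, a progression documented in that month suggests that therapy began later. Elsewhere the SAP does check imputed dates against known ones: adverse-event dates against dosing and death (2.7.1), medication dates against first dosing (2.7.2), and diagnosis date against first prior therapy (2.7.3). Neither 2.7.4, 5.3.1 nor Table 2 has such a check against progression. SAP 5.1.3, which rules out imputing missing efficacy values, does not override the date rule.

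PFS is second in the superiority hierarchy of SAP 5.1.1. An event lost in this way is lost because the subject progressed and switched quickly. That is informative censoring, and it raises the Kaplan-Meier PFS and DOR curves in whichever arm it occurs.

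**Working it through.** The plan states no PFS event count, no PFS power and no share of partial dates, so there is no figure of its own to reproduce.

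**Rule.** Let L be the last dose, P the first progression date, C the confirming assessment, T the true therapy start and S the imputed start.

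- Same month and year for T and L: S = L + 1 (or the stop-date day, if earlier).
- Otherwise: S = first day of the month of T.
- PFS event if P ≤ S (SAP Table 2). If the algorithm applies Protocol Table 5 literally, C ≤ S is also needed.

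**Worked records** (illustrative dates, day of T taken as missing).

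| L | P | C | T | S | P ≤ S | C ≤ S |
|---|---|---|---|---|---|---|
| 10 Jun | 12 Jul, bone lesion | not needed | 24 Jul | 1 Jul | no | n/a |
| 10 Sep | 8 Oct | 15 Oct | 22 Oct | 1 Oct | no | no |
| 1 Oct | 15 Oct | 22 Oct | 29 Oct | 2 Oct | no | no |
| 2 Oct | 2 Oct | 12 Oct | 20 Oct | 3 Oct | yes | no |
| 10 Sep | 10 Sep | 20 Sep | 10 Oct | 1 Oct | yes | yes |

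Row 1 does not depend on confirmation, because Protocol 9.2.6 requires no repeat films when radiographic progression is obvious. In row 2, on a 28-day schedule, PFS is censored at 10 September instead of being an event on 8 October. Row 3 shows the last-dose + 1 branch failing. Row 4 is lost only by the confirmation route. Row 5 is unharmed, because progression and confirmation fell in an earlier month.

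**When nothing is lost.** Suppose L ≥ C. In the same month, S = L + 1 > C. In a later month, the first of that month is after L, so S > L ≥ C. The plain rule therefore cannot lose the event. Similarly, L ≥ P protects the first progression date. The stop-date branch is outside this guarantee, since it uses only a day number: last dose 20 October and therapy stopped 2 November gives S = 2 October.

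**How often, given a missing day.** Simulation of 200,000 records per scenario, P uniform over one year. The gaps are assumptions; the documents give none.

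| L relative to P | P to C (days) | C to T (days) | S before P | S before C |
|---|---|---|---|---|
| 28 days before | 1–7 | 1–14 | 59% | 72% |
| 28 days before | 7–28 | 1–14 | 19% | 72% |
| 28 days before | 7–28 | 14–42 | 0.7% | 14.5% |
| 14 days before | 7–14 | 1–14 | 37.5% | 72% |
| same day | 1–7 | 1–14 | 0 | 62% |
| same day | 7–28 | 1–14 | 0 | 72% |
| same day | 7–28 | 14–42 | 0 | 14.4% |
| L on or after C | any | any | 0 | 0 (by the argument above) |

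**Overall share lost** = share of start dates with a missing day × share of those affected.

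- Assuming 1% to 10% missing and about 10% to 70% affected: 0.01 × 0.10 = 0.1% to 0.10 × 0.70 = 7% of progressions followed by new therapy.
- First-progression route alone, taking every subject as last dosed before P: 0.01 × 0.007 = 0.007% to 0.10 × 0.59 = 5.9%.

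Both ranges omit subjects dosed through confirmation, whose loss is zero, so they overstate the effect to that extent.

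**The case against.** The strongest reply is that the protocol's normal path avoids the problem. Protocol 10.1 continues treatment until progression is confirmed. M-protein samples are taken before dosing on Day 1 visits and read centrally, so a subject will often be dosed on the day of the sample that later shows or confirms progression. This stands. It confines the problem to doses held, missed or already stopped, and to confirmation by an unscheduled repeat after the last dose.

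The confirmation column above depends on the algorithm in SAP Attachment 2, which is not in the supplied text. SAP Table 2 dates the event by its earliest indication and does not mention confirmation. That route is therefore conditional; the first-progression route is not.

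Data queries (Protocol 17.5 and 17.6) may recover some missing days, and SAP 5.3.1.2 tabulates reasons for censoring. These would make cases visible but would not change how they are classified.

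Three stronger readings are tempting, and the documents do not support them:

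- A reader might infer from the 60% to 70% cells that PFS loses a large share of its events. Those cells apply only to missing-day records, rest on assumed gaps and mostly use the conditional route.
- A reader might infer that the hazard ratio is biased towards one arm. Nothing suggests different rates by arm, so no direction can be stated.
- A reader might infer harm to the ORR co-primary or to safety reporting. No ORR problem is shown, and an early cut-off there guards against crediting responses on the next therapy. The adverse-event window in SAP 6.1 does close at 30 days after the last dose "or the day prior to start of subsequent therapy, whichever is earlier", but events judged related count whatever their start date.

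**Conclusion.** The concern holds in a limited form. SAP 2.7.4 and Table 2 together can censor a documented progression when three things coincide: the day of next therapy is missing, progression falls in the same month as that therapy, and the subject was not dosed at or after the progression visit. If Attachment 2 applies Protocol Table 5 literally, the same can happen when only the confirmation falls after the imputed day. The mechanism follows from the text.

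Its size does not: the share of missing days, the gaps between events and the dosing pattern around progression are all assumptions. The effect is probably small, within the ranges shown. What can be said firmly is that events may be lost through informative censoring in the second endpoint of the hierarchy and in DOR. A change is worth making because the rule gives a wrong result in identifiable cases and costs little to correct.

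**What to change.** In SAP 2.7.4, add that when only the day is missing, the imputed start may not be earlier than a documented progression, or its confirming assessment, in that same month. Cap the date at the end of the month, the therapy stop date and death. State that an assessment on the imputed day counts as preceding therapy, as Table 2 already does for progression. Row 1 of the worked records then becomes an event on 12 July, and row 2 an event on 8 October.

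Do not use other disease assessments as a floor. The End-of-Treatment visit includes serum and urine M-protein, and Protocol 9.1.3 asks only for every effort to hold it before subsequent treatment. A sample drawn after the switch would push the start too late and could credit a next-therapy response to study drug. For the same reason, keep the existing earliest-day rule for the response cut-off in SAP 5.2.1.

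Report the number of imputed start dates by arm, and add a PFS sensitivity analysis using the latest possible day.

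The cost is a sentence, a small programming change and one extra analysis, with no new data. There are two drawbacks. A progression actually observed after an early, undated switch would count as an event, and time to next therapy becomes slightly longer for a few subjects.

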#### **2.8. General Analysis Method**

In general, continuous variables will be summarized using descriptive statistics such as mean, standard deviation, median and range. Categorical variables will be summarized using frequency and percentage. For time-to-event variables, which is defined as from the date of randomization to the date of the event, the Kaplan-Meier method will be used for descriptive summaries. For the calculation of time-to-event and duration-of-event variables, the difference between the start date and the end date plus 1 day will be used.

## 2.9. Other General Definitions

### 2.9.1. Measurable Disease of Multiple Myeloma at Baseline and Measurable Type

Measurable disease at baseline is defined by any of the following:

- IgG multiple myeloma: Serum M-protein level  $\geq 1.0$  g/dL or urine M-protein level  $\geq 200$  mg/24 hours; or
- IgA, IgD, IgE, IgM multiple myeloma: serum M-protein level  $\geq 0.5$  g/dL or urine M-protein level  $\geq 200$  mg/24 hours; or
- Light chain multiple myeloma without measurable disease in the serum or the urine: Serum immunoglobulin free light chain (FLC)  $\geq 10$  mg/dL and abnormal serum immunoglobulin kappa lambda FLC ratio.

If a subject meets the criteria for serum M-protein, the measurable disease type is serum; otherwise, if a subject meets the criteria for urine M-protein, the measurable disease type is urine; otherwise if a subject meets the criteria for FLC, the measurable disease type is FLC. If a subject meets both of the criteria for serum M-protein and urine M-protein, then the measurable disease type is “serum and urine”.

### 2.9.2. Type of Multiple Myeloma

Type of myeloma for a subject is determined by serum heavy chain or serum FLC or urinary FLC. Serum heavy chain refers to serum immunoglobulin of IgG, IgA, IgM, IgD, or IgE. Serum and urine FLC refers to kappa or lambda type.

A subject will be classified as IgG type of myeloma if any reported result contains serum heavy chain ‘IgG’ regardless of FLC reported, similarly for IgA, IgM, IgD and IgE type. A subject will be classified as the light chain type of myeloma if any reported result is either ‘Lambda light chains’ or ‘Kappa light chains’ but without heavy chain reported. A subject will be reported as ‘biclonal’ if the distinct test results contain different heavy chain values or different FLC values. A subject will be classified as “Negative immunofixation” if the reported result is “Not Detected” and with no serum heavy chain, serum light chain and urine light chain reported.

### 2.9.3. International Staging System (ISS)

ISS staging is based on the combination of serum  $\beta 2$ -microglobulin (B2MG) and serum albumin (ALB) at baseline.

- Stage I:  $\beta 2$ -microglobulin  $< 3.5$  mg/L and serum albumin  $\geq 35$  g/L
- Stage III:  $\beta 2$ -microglobulin  $\geq 5.5$  mg/L
- Stage II: Neither stage I nor stage III
- ( $\beta 2$ -microglobulin  $< 3.5$  mg/L but serum albumin  $< 35$  g/L, or  $\beta 2$ -microglobulin  $\geq 3.5$  mg/L to 5.5 mg/L irrespective of the serum albumin level)

#### **2.9.4. Hepatic Function**

Hepatic impairment is classified into 4 levels per NCI organ dysfunction criteria, using baseline total bilirubin and Aspartate Aminotransferase (AST):

- Normal: total bilirubin  $\leq$  ULN and AST  $\leq$  ULN
- Mild: (total bilirubin  $\leq$  ULN and AST  $>$  ULN) or (ULN  $<$  total bilirubin  $\leq$  1.5 $\times$ ULN)
- Moderate: 1.5 $\times$ ULN  $<$  total bilirubin  $\leq$  3 $\times$ ULN
- Severe: total bilirubin  $>$  3 $\times$ ULN

#### **2.9.5. Relapsed Disease**

Relapsed disease is defined as an initial response to previous treatment, followed by progressive disease (PD) by IMWG criteria  $>$ 60 days after cessation of treatment.

#### **2.9.6. Refractory Disease**

Refractory disease is defined as  $<$ 25% reduction in M-protein or confirmed PD by IMWG criteria during previous treatment or  $\leq$ 60 days after cessation of treatment.

#### **2.9.7. High Risk/Standard Risk Cytogenetics**

The high risk and standard risk cytogenetics are defined as follows:

- High risk: subjects that are positive for any of del17p, t(14;16), t(4;14) by FISH/Karyotype
- Standard risk: subjects with sufficient cytogenetic testing to rule out presence of deletion of del17p, t(14;16), and t(4;14)

A subject will be classified as “Undetermined” if a subject had either no cytogenetic testing performed or had cytogenetic testing performed but risk categorization could not be determined.

#### **2.9.8. Time since Initial Multiple Myeloma Diagnosis**

Time since initial multiple myeloma diagnosis to randomization in years is calculated as date of randomization – date of initial MM diagnosis + 1, divided by 365.25.

#### **2.9.9. End of Follow-up and Duration of Follow-up**

The end of follow-up is defined as the maximum date of the following study evaluations: labs (hematology, chemistry, immunology), adverse events, vital signs, ECOG performance status, PRO assessment, bone marrow cytogenetics, lytic bone lesions, extra-medullary plasmacytomas, study drug administration, ECG, pre-dose medications, post-dose medications, concomitant medications, subsequent therapy, medical encounters, clinical events/disease response per investigator and date of last known to be alive. For subjects who died on study, the end of follow-up is the date of death. For subjects who died after the end of study, the end of follow-up will be set to the maximum date derived above.

Duration of follow-up (in months) = the date of end of follow-up - the date of randomization + 1, divided by 365.25/12.

## 2.10. Definition of Subgroups

In general, subgroup analyses on the pre-specified subgroups in Table 1 will be performed for the primary efficacy endpoint ORR, major secondary endpoint of rate of infusion-related reactions (IRRs), and safety endpoints treatment-emergent adverse event (TEAE). Additional exploratory subgroup analyses may be performed for selected efficacy and/or safety endpoints.

